1 INTRODUCTION

The 2018 International Contact Lens Prescribing report¹ describes 32% of soft lenses are prescribed on a daily disposable (DD) basis worldwide (27% in US), compared with 13% and 51% on a one-to-two week and monthly replacement schedule, respectively (30% and 41% in US). There has been an upward trend in prescribing daily disposables for several years.²

Until recently, DD lenses were mainly available in a hydrogel material. However, in line with the increasing market share of DD lens modality, more and more new silicone hydrogel (SiHy) DD lenses are becoming available. One of these new SiHy DD lenses are Precision1 lenses that has been recently introduced by Alcon.

This study will evaluate the performance of Alcon's Precision1 (CONTROL lens) compared to CooperVision's MyDay (TEST lens). All participants will habitually wear soft contact lenses, but they do not have to habitually wear daily disposable lenses. Participants with a history of wearing one of the study contact lenses are not eligible for this study. [REDACTED]

[REDACTED]. All lenses used in this study are spherical, silicone hydrogel daily disposables lenses that are approved by Health Canada.

2 OBJECTIVES

The objective of the study is to evaluate and compare the performance of the study TEST lens to the CONTROL lens, when worn on a daily disposable modality over a period of approximately one week each.

The primary outcome variable of this study is:

- Overall lens fit acceptance at the 1-week follow-up visit.

The secondary outcome variables are:

- Centration (optimal, slight decentration, moderate decentration but not encroaching limbus, excessive & occasionally encroaching limbus), collected at dispense & 1-week visit;
- Post-blink movement in primary gaze, mm, collected at dispense & 1-week visit;
- Push-up tightness in primary gaze (0-100), collected at dispense & 1-week visit.

Participants will be randomized to wear either the test or the control lens first. All lenses will be worn in a daily disposable lens wear modality for one week (-1/+3 days). The study involve up to 5 scheduled visits. The study design is shown in Figure 1.

[figure not shown]

Figure 1: Study Design, visits 1 & 2 may be on a single day, also visits 3 & 4 may be on a single day.

Visit 1: Includes screening, baseline assessments, fitting of both study lenses.

Visit 2: Dispense lens pair #1 (either test or control lens, randomized).

Visit 3: 1-week follow-up assessment of lens pair #1

Visit 4: Dispense of lens pair #2 (either test or control lens)

Visit 5: 1-week follow-up assessment of lens pair #2 and study exit.

- Participants will complete the following in-office subjective ratings on paper using a numeric rating scale (0 – 10) at visits 3 and 5 for each lens type:

- Lens handling;

- [Redacted]
- [Redacted]
- [Redacted]
- [Redacted]

[Redacted]

[Redacted]

[Redacted]

[Redacted]

- [Redacted]
- [Redacted]
- [Redacted]
- [Redacted]

- [REDACTED]
- [REDACTED]
- [REDACTED]
- [REDACTED]
- [REDACTED]

4.1.3 RANDOMIZATION

A randomization schedule will be generated using a web-based program: (for example www.randomization.com) by CORE's Data management team, and provided to the research assistants for the study. The schedule will determine the order of lens wear for participants in the study. Study investigators will remain masked to the randomization schedule until the study is completed and the database has been locked.

4.1.4 MASKING

Participants will be masked to the lens assignment. Lenses dispensed to participants may be either over-labelled or have part of the label obscured, however the safety information shall be clearly visible. Investigators will be masked as much as possible however it may not be possible to fully mask the investigators, because identifying lens markings may be visible during the biomicroscopy examination.

5 STUDY POPULATION

5.1.1 SAMPLE SIZE CALCULATION

Sample size was calculated using the mean overall fit acceptance from the previous pilot BOXER study [REDACTED]

A sample size of 34 is recommended to detect a mean difference between lens Overall fit acceptance of 0.2 units on the 0 to 4 scale using a standard deviation of 0.4 with 80% power and alpha 0.05 in a two-tailed t-test. Therefore, it is recommended that at least 38 subjects are dispensed in the MIKI study, with a target of 34 to complete.

5.1.2 NUMBER OF PARTICIPANTS

Participants will be screened using CORE records and advertising approved by the UW Office of Research Ethics. Approximately 38 participants will be dispensed with study products in the study, with a target of 34 completing the study.

A documented informed consent process will be conducted with all participants prior to their enrolment in the study and prior to any data collection or measurements.

5.1.3 INCLUSION AND EXCLUSION CRITERIA

A person is eligible for inclusion in the study if he/she:

1. Is at least 17 years of age and has full legal capacity to volunteer;
2. Has read and signed an information consent letter;
3. Is willing and able to follow instructions and maintain the appointment schedule;
4. Habitually wears soft contact lenses in daily wear, for minimum of 6-months;
5. Is correctable to a visual acuity of 20/40 or better (in each eye) with the study lenses;
6. Has an astigmatism of ≤ 1.00 D in subjective refraction;
7. Can be fit with study contact lenses with a power between -2.00 and -5.00 DS;
8. Demonstrates an acceptable fit with the study lenses;
9. Habitually wears single vision soft contact lenses for at least 8 hours per day, 5 days a week, and is willing to wear contact lenses for at least 12 hours a day in the study.

A person may be excluded from the study if he/she:

1. Is participating in any concurrent clinical or research study;
2. Has any known active* ocular disease and/or infection;
3. Has a systemic condition that in the opinion of the investigator may affect a study outcome variable;
4. Is using any systemic or topical medications that in the opinion of the investigator may affect a study outcome variable;
5. Has known sensitivity to the diagnostic pharmaceuticals to be used in the study;
6. Is pregnant, lactating or planning a pregnancy at the time of enrolment because the associated hormonal changes cause changes in the tear layer which impact contact lens comfort. Verbal confirmation at the screening visit is sufficient;
7. Has undergone refractive error surgery or any intraocular surgery, including cataract surgery;

8. Is an employee of the Centre for Ocular Research & Education;
9. Has participated in the BOXER [REDACTED] or BASSET [REDACTED] Study;
10. Has any history of wearing one of the study contact lenses;
11. Has participated in any clinical trials within a week prior to the study.

* For the purposes of this study, active ocular disease is defined as infection or inflammation, which requires therapeutic treatment. Mild (i.e. not considered clinically relevant) lid abnormalities (blepharitis, meibomian gland dysfunction, papillae), corneal and conjunctival staining and dry eye are not considered active ocular disease. Neovascularization and corneal scars are the result of previous hypoxia, infection or inflammation and are therefore not active.

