5.3 SCHEDULED AND UNSCHEDULED VISITS

This study has 5 visits. The visits are as follows:

- **Visit 1:** Screening, baseline assessments, fitting of both study lenses.
- **Visit 2:** Dispense lens type #1 (normally combined with Visit 1)
- **Visit 3:** 1-week follow-up assessment of lens type #1 (6 to 10 days after Visit 2), worn lens collection
- **Visit 4:** Dispense of lens type #2 (normally combined with Visit 3)
- **Visit 5:** 1-week follow-up assessment of lens type #2 and study exit (6 to 10 days after Visit 4), worn lens collection

A scheduled follow-up visit may only take place when the participant attends wearing the study lenses for 6-8 hours. If this is not the case and the participant is not experiencing any problems with the lenses, the appointment will be rescheduled, ideally within the visit window.

Visits that fall outside of the specified visit windows will be designated as protocol deviations and at the end of the study, the data collected during protocol deviations will be assessed for their suitability to be included in the analysis population.

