5.3.3 DISPENSING LENS TYPE #1 (VISIT 2)

The procedures to be performed are outlined below:

1. The participant will be assigned a randomization ID (by the research assistant) and the first pair (lens pair #1) of contact lenses (either test or control lens) will be selected according to the randomization table.
2. Lens pair #1 will be provided to participants in a manner which does not unmask the participant or investigator, as described in Section 5.2.4.
3. The participant will insert the lenses.
4. The contact lenses will be allowed to settle for 10 minutes.
5. The participant will be asked to give subjective binocular ratings for:
 - a. [REDACTED]
6. [REDACTED]
7. [REDACTED]
8. Lens [REDACTED] fit will be assessed and graded according to the following grading scales:
 - a. [REDACTED]
 - b. [REDACTED]
 - c. Lens push-up tightness in primary gaze (0 – 100 scale);
 - d. Centration in primary gaze (scale: optimal, slight decentration, moderate decentration but not encroaching limbus, excessive & occasionally encroaching limbus);
 - e. Post-blink movement in primary gaze (mm);
 - f. Overall fit acceptance (0 – 4 scale, and reason if Grade 2 or less).
9. [REDACTED]

- b) [REDACTED]
 - c) Lens push-up tightness in primary gaze (0 – 100 scale);
 - d) Centration in primary gaze (scale: optimal, slight decentration, moderate decentration but not encroaching limbus, excessive & occasionally encroaching limbus);
 - e) Post-blink movement in primary gaze (mm);
 - f) Overall fit acceptance (0 – 4 scale and reason if Grade 2 or less).
6. Study lens collection at 1-week: investigator will remove study lenses from participant eyes while wearing a pair of disposable non-latex medical grade gloves. The lenses will be rinsed and stored according to sponsor instructions which will be provided at a later date. They will be labeled with study name, participant study ID, eye, visit# and date without any identifying characteristics. They will be stored in a -80 degrees centigrade freezer and shipped to the sponsor when all participants have completed the study.
 7. Slit lamp biomicroscopy assessments (see 5.3.2 for details).
 8. There will be a washout of 10 minutes after lens removal if Visit 4 is to be concurrent with this visit.

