5.3.7 STUDY EXIT

The study exit form will be completed when a participant exits the study. This form will be completed either at study completion, or if the participant is discontinued from the study at another time. A study exit form must be completed for all participants who have taken a study ID number. If in the opinion of the investigator post-study follow-up visits are required, the exit form will be completed after the last follow-up visit.

[REDACTED]

After the exit assessments have been completed, the participant and investigator will complete the study completion and remuneration forms. At this time the participant will be considered as having exited the study.

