5.4 STUDY PROCEDURES

The summary of the visits and study procedures to be conducted at scheduled visits is listed in Table 3.

Table 3: Summary of procedures to be conducted at scheduled visits

	V1 Screen & fit	V2 Disp lens#1	at-home ratings (days 1,3, 5) lens#1	V3 1-week progress lens#1	V4 Disp lens#2	at-home ratings (days 1,3, 5) lens#2	V5 1-week progress lens#2	V-Exit
Consent process	x							
CL history and/or lens wear schedule	x	x		x	x		x	
Health & medication	x	x		x	x		x	
Review any problems with eyes/study lenses				x			x	
[REDACTED]								+
[REDACTED]								
[REDACTED]	x							

	V1 Screen & fit	V2 Disp lens#1	at-home ratings (days 1,3, 5) lens#1	V3 1-week progress lens#1	V4 Disp lens#2	at-home ratings (days 1,3, 5) lens#2	V5 1-week progress lens#2	V-Exit
Study lens fitting (both lens types)	x							
Dispense study CLs*		x			x			
[REDACTED]	x	x		x	x		x	
Trial lens fit	x							
[REDACTED]		x		x	x		x	
Study CL fit assessment	x	x		x	x		x	
Complete 'in-office' subjective ratings		x		x	x		x	
[REDACTED]							█	
[REDACTED]			█			█		
[REDACTED]				x			x	
Worn lens collection				x			x	
[REDACTED]	x	x**		x	x**		x	x**
Study completion and Exit								x

* Additional lenses may be dispensed at scheduled or U/S visits if there is lens defect, or lens damage or if there is a valid reason (e.g. lenses dropped or misplaced etc.)

** Not required if visit concurrent with previous one.

¹High Contrast High Illumination

5.5 [REDACTED]

[REDACTED]

[REDACTED]

[REDACTED]

[REDACTED]

[REDACTED]

[REDACTED]

[REDACTED]

[REDACTED]

[REDACTED]

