9 DISCONTINUATION FROM THE STUDY

Participants discontinued from a study will be reimbursed \$20 per hour for their active involvement in the study (including the initial screening visit). Participants will be discontinued at the discretion of the investigator or sponsor in consideration of participant safety or protocol compliance, or at discretion of the participant. The following is a list of possible reasons for discontinuation from the study:

- Screening failure: Participants will be discontinued if they do not meet the inclusion and exclusion criteria outlined in section 5.1.3.
- Unacceptable performance with products to be used in study: Participants may be discontinued if they are unable to achieve acceptable comfort and /or vision with the study products.
- Positive slit lamp finding: Participants may be permanently discontinued from the study depending on the severity of the condition and on the judgement of the investigator.
- Adverse event: If a participant experiences an adverse event during the study they may be discontinued based on the clinical judgement of the investigator.
- Symptoms: If the participant has persistent symptoms they may be discontinued based on the clinical judgement of the investigator.
- Disinterest, relocation or illness: The participant may choose to discontinue due to reasons within or beyond their control.
- Violation of protocol or non-compliance: The participant will be discontinued if they are unable or unwilling to follow the protocol specified visit schedules and/or study procedures.
- Instillation of topical ocular medication: The participant will be discontinued if they elect to use a topical ocular medication during the study unless that topical ocular medication is prescribed for a limited duration (less than two weeks) to treat a transient condition; in this case the participant may remain an active participant (at the discretion of the investigator) after stopping topical ocular medication following resolution of the ocular condition).
- Lost to follow-up: The participant will be discontinued if they cannot be contacted and do not return for a final exit visit, and if the investigator has made a reasonable effort to contact the participant for a final study visit.
- Premature termination of the study by the sponsor, CORE or the Office of Research Ethics at the University of Waterloo.

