A discontinuation form, stating the reason for discontinuation will be completed, which requires the signatures of both the participant and the investigator, except where the participant is lost to follow-up in which case only the signature of the investigator is required.

When a participant chooses to discontinue from the study they will be given the opportunity to withdraw their data from the statistical analysis. This choice will be captured on the discontinuation form.

All discontinuations including their reasons will be included in the final report.

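### Does requiring an acceptable initial fit in both lenses undermine a primary outcome that is itself fit acceptance?

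*Combined protocol and SAP*

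**What the plan says.** All references are to the combined protocol and SAP.

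- Section 5.1.3, inclusion 8, requires that a person "Demonstrates an acceptable fit with the study lenses". The plural, together with the description of Visit 1 in section 5.3 ("Screening, baseline assessments, fitting of both study lenses"), makes both lenses the natural reading.
- Section 5.3.3 places randomization after that, at Visit 2: "The participant will be assigned a randomization ID (by the research assistant").
- Section 2 names the primary outcome: "Overall lens fit acceptance at the 1-week follow-up visit". Section 5.3.3 grades it from 0 to 4 and asks for a reason at grade 2 or below.
- Table 3 in section 5.4 marks "Study CL fit assessment" at Visit 1 as well as at the dispensing and 1-week visits.
- Section 9 deals with people who fail entry: "Screening failure: Participants will be discontinued if they do not meet the inclusion and exclusion criteria outlined in section 5.1.3". It requires a form giving the reason, and adds: "All discontinuations including their reasons will be included in the final report".
- Section 5.3.7 has a separate exit form: "A study exit form must be completed for all participants who have taken a study ID number". Section 14 equates holding a study ID with being randomized.
- Trial-fit steps 13d and 13e and the label of one row of Table 6 (section 12.1) are redacted.

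**The concern.** The entry filter is an early reading of the primary endpoint. If one lens fits worse at first try, the people who would show this most clearly are removed before randomization, and the 1-week difference is measured among those for whom both lenses already worked. The difference could then be smaller than among everyone who tried both lenses, and the initial failures are themselves information about fit.

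The reporting also looks thin. Exit forms cover only people with a study ID, status reports give overall counts, and the readable part of section 12.1 describes no analysis of the Visit 1 fit. A reader might be unable to tell whether the primary result carries over to wearers in general.

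**Working it through.** **1. The plan's own figure.** Section 5.1.1 gives a difference of 0.2, SD 0.4, two-sided alpha 0.05 and 80% power, and arrives at 34 completers. Reading 0.4 as the SD of the within-person difference, the noncentrality at n = 34 is (0.2/0.4) × √34 = 2.92. Noncentral-t power is 80.8% at n = 34 and 79.5% at n = 33, so 34 reproduces. Dispensing to 38 allows for 4/38 = 10.5% loss. The concern disputes neither number.

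**2. Validity.** Let S_T and S_C be the Visit 1 fits and D = Y_T − Y_C the 1-week difference in the same person. Selection depends on S_T and S_C only, both observed before the wearing order is assigned. The order is therefore randomized within the selected group, and the mean of D given acceptable S_T and S_C is a proper target. Fit at 1 week can still vary, and differences above the cut-off or arising during wear remain visible. What changes is the population, which inclusion 8 states.

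**3. Possible attenuation.** The readable text gives no cut-off, grading step or failure rate, so everything here is assumed except the 0.2 and the 0.4. Simulated model: lens means 0.2 apart, centred on 3.1, 3.3 or 3.5; person SD 0.3 or 0.5; person-by-lens SD and visit SD of 0.245 and 0.14, or 0.20 and 0.20. Each pair gives a paired SD of 0.40, for example √(2 × (0.20² + 0.20²)) = 0.40. Grades are rounded and limited to 0–4.

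| Rule applied to both lenses at Visit 1 | Grade step | Kept | Shrinkage of the 1-week difference |
|---|---|---|---|
| Grade 2 or more | 0.25 | 97–100% | 0–2% |
| Above grade 2 | 0.25 | 92–99.9% | under 5% |
| Grade 3 or more | 0.25 | 53–88% | 8–23% |
| Grade 3 or more | 1 | – | 1–17% |

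With whole grades, above 2 and at least 3 are the same rule, so the last row covers both. That row has a paired SD of 0.53–0.58, which does not match the plan's 0.4.

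In the 23% setting the difference falls from 0.197 to 0.151, but the SD also falls, from 0.407 to 0.371. The standardised effect goes from 0.197/0.407 = 0.484 to 0.151/0.371 = 0.407, a loss of about 16%.

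A second model, without rounding (per-lens SD 0.4, between-lens correlation 0.5, above grade 2 required), gives the same picture. With the better lens at mean 3.5 almost nobody is lost and the difference stays at 0.20. At 3.0 about 3% are lost and it is 0.19–0.20. At 2.5 about 27% are lost and it is 0.17–0.18. With n = 34 and SD 0.4, power is 76.7% at 0.19, 72.1% at 0.18 and 67.2% at 0.17.

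**4. What a by-lens Visit 1 table would show.** With assumed counts of 4 one-lens-only wearers among 42 fitted, the proportion is 4/42 = 9.5%, exact 95% CI 2.7–22.6%. For the mean grade difference, the half-width is t(41) × 0.4/√42 ≈ 2.02 × 0.0617 = 0.125, more than half of the planning difference of 0.2. The readable text does not describe the Visit 1 fitting order as randomized, and wear at that visit is short.

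**The case for a change.** The best case for acting is that the objective is to compare the two lenses, fit is primary, and how many wearers can be fitted acceptably with each lens is basic fit information. In the quarter-unit model with a grade 3 cut-off, 11–30% of wearers are acceptable in one lens only, and they split about 3.4–3.8 to 1 towards the better-fitting lens, so those removed carry a direction. The count would be cheap, because consent precedes any measurement and Table 3 already schedules the assessment. If it is not written down in advance, reporting it becomes discretionary.

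Part of this stands: no readable text promises initial fit failures by lens, and a line in the participant flow would do no harm. The rest does not make it a defect. Section 2 asks how the lenses perform when worn for about a week each, so people never dispensed a lens fall outside that question. The exit-form argument does not show that failures go undocumented, since section 9 counts screening failure as a discontinuation with its own form and reason. Silence in section 12.1 is weak evidence: no fit variable is legible in Table 6, not even the primary one. The material end of the attenuation range needs a grade 3 cut-off, and the only readable anchor is the request for a reason at grade 2 or below.

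**Conclusion.** The concern describes the plan correctly but calls for no change. Requiring a workable fit in both lenses before dispensing is a fair trade-off in a two-period crossover, because each participant must wear both. The comparison is valid for the wearers enrolled, the entry rule identifies them, and screening failures with reasons are already due in the final report. The missing by-lens split is a reporting detail that an analyst can add to the participant flow from the discontinuation reasons and Visit 1 records, as far as these name the lens. It would leave the sample size, the primary analysis and its conclusion unchanged.

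The size of any attenuation is not determinable from the readable text. It is negligible if initial failures are rare, and material only if they are common and unequal between lenses, for which the documents give no evidence. If the pilot behind the planning figures had a similar entry rule, the 0.2 is already conditional on acceptable fit and planned power is unaffected; those details are redacted. The verdict rests on reading inclusion 8 as covering both lenses and on the redacted trial-fit steps not contradicting the visible text.

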5.1.4 REPEATED SCREENINGS

In some circumstances, a repeated screening may need to be scheduled. The maximum total number of screenings permitted will be 3 ie. 2 re-screens. Examples of reasons include, but are not limited to:

1. Incomplete information available at time of screening to determine eligibility (e.g. current lens brands worn, history from current eye care practitioner etc.);
2. Study procedures unable to be completed in time scheduled for visit;
3. Study products not available at the time of the screening visit;
4. The short term use of medications (e.g. antibiotics, antihistamines etc.);
5. Reassessment of baseline ocular conditions (e.g. corneal and/or conjunctival staining, scars etc.).

